16.1.5. SUPPLEMENTARY ANALYSES FOR PRIMARY EFFICACY ENDPOINT

The following supplementary analyses to the main analysis of the primary efficacy endpoint will be performed:

- The main analysis to the primary efficacy endpoint will be repeated (refer to Section 16.1.3) but without country (region; refer to Section 7.5) included as stratification variable;
- The main analysis of the primary efficacy endpoint will be repeated but without the requirement for follow-up confirmation. That is, for this analysis, patients will be considered as having met the event as soon as they reach a score of 6, 7 or 8 on the 8-point ordinal scale, regardless of if they subsequently worsened or were re-hospitalized before or on Day 29, exception of patients with a score of 7 discharged to hospice care who will

still be considered as not having the event;

- The main analysis of the primary efficacy endpoint will be repeated for each subgroup defined in Section 7.7. For subgroups corresponding to one of the factors included in the main model, the corresponding factor will be excluded from the model. For example, the remdesivir use at baseline (yes/no) stratification variable as captured on the IWRS will not be included in the model for the analysis of the patients who received remdesivir at randomization as captured on the IWRS subgroup, and analysis of the patients who did not receive remdesivir at randomization as captured on the IWRS subgroup.

[figure not shown]
16.2. SECONDARY EFFICACY

16.2.1. SECONDARY EFFICACY ENDPOINTS

16.2.1.1. Incidence of Patients with Oxygen-Free Recovery at Day 29

The first key secondary efficacy endpoint is the incidence of patients with oxygen-free recovery at Day 29, defined as the proportion of patients who were alive, discharged, and not receiving supplemental oxygen at Day 29.

1. The alive status of a patient at Day 29 (yes or no) will be determined as follows based on data captured on the *Death Details* page of the eCRF: patients who died before or on Day 29 will be considered as not being alive at Day 29 while patients without any data captured on this page of the eCRF before or on Day 29 but with some data captured on any other page of the eCRF on or after Day 29 will be considered to be alive at Day 29;
2. The patient’s discharge status (yes or no) at Day 29 will be established as follows based on data collected on the *Ordinal Scale for Clinical Severity* page of the eCRF: a patient will be considered as being discharged at Day 29 if 1) their ordinal scale score is 7 at Day 29 and patient was not discharged to hospice care or 2) their ordinal scale score is 8 at Day 29. Discharge to hospice care status will be verified based on data collected on the *Hospitalization* page of the eCRF. To do so, the outcome of the hospitalization record with the latest stop date before or on Day 29 will be examined. The hospitalization outcome of that record should not be ‘Home: Hospice Care’ or ‘Hospice Medical Facility’ for a patient with an ordinal scale score of 7 at Day 29 to be considered as discharged at that time. Patients who discontinued early from study before Day 29 will be considered as having a missing discharged status at Day 29;
3. The patient’s oxygen-free status (yes or no) at Day 29 will be determined as follows: data collected on the

Supplemental Oxygen and Mechanical Ventilation page of the eCRF will be examined to verify if the patient has a record where the start date of supplemental oxygen/mechanical ventilation is before or on Day 29 and stop date of supplemental oxygen/mechanical ventilation is after Day 29* or is ongoing at Day 29. Patients without such record will be considered as being oxygen-free at Day 29 while patient with such record will be considered as being not oxygen-free at Day 29. Patients who discontinued early from study before Day 29 will be considered as having a missing oxygen-free status at Day 29.

* That is, patients who stopped receiving supplemental oxygen/mechanical ventilation on Day 29 will be considered as being oxygen-free at Day 29.

All three criteria (alive, discharged, and not receiving supplemental oxygen at Day 29) must be fulfilled for a patient to be considered as having an oxygen-free recovery at Day 29. That is, as soon as a patient does not fulfill at least one of the three criteria, he/she will be considered as not having an oxygen-free recovery at Day 29, regardless of the status of the other criteria. Should the status of one of the three criteria be missing while the two other criteria are fulfilled or missing, patients' oxygen-free recovery at Day 29 will be considered as missing.

[figure not shown]
Scenario	Alive at Day 29 (as per step 1)	Discharge at Day 29 (as per step 2)	Oxygen-free at Day 29 (as per step 3)	Oxygen-free Recovery at Day 29
1	Alive	Yes	Yes	Yes
2	Dead	Yes, No, Missing	Yes, No, Missing	No
3	Alive, Dead, Missing	No	Yes, No, Missing	No
4	Alive, Dead, Missing	Yes, No, Missing	No	No
5	Missing	Yes, Missing	Yes, Missing	Missing
6	Alive, Missing	Missing	Yes, Missing	Missing
7	Alive, Missing	Yes, Missing	Missing	Missing

Refer to Section 16.2.2.1 for handling of missing oxygen-free recovery at Day 29 status.

16.2.1.2. Incidence of Patients with ≥ 2-point Improvement from Baseline or Fit for Discharge on the Ordinal Scale at Day 29

The second key secondary efficacy endpoint is the incidence of patients with ≥ 2-point improvement from baseline or fit for discharge on the 8-point ordinal scale for clinical severity (refer to Section 16.1.1) at Day 29, where fit for discharge is defined as having a score of 6, 7 or 8 on the ordinal scale for clinical severity. Patients with an ordinal scale score of 7 must not have been discharged to hospice care to be considered as fit for discharge.

By endpoint definition, patients with an ordinal scale score of 6, 7 (but not discharged to hospice care) or 8 at Day 29 will be considered as having met the event (yes) at Day 29, regardless of their change from baseline in ordinal

scale score, while patients with a score of 7 discharged to hospice care will be considered as not having met the event, also regardless of their change from baseline in ordinal scale score. For patients hospitalized and not considered as fit for discharge at Day 29 i.e., patients with an ordinal scale score < 6, the ‘≥ 2-point improvement from baseline’ requirement (yes or no) will be established based on the patient’s change from baseline in the ordinal scale at Day 29, where change from baseline will be computed as defined in Section 6.5.

Refer to Section 16.2.2.1 for handling of missing ≥ 2-point improvement from baseline or fit for discharge on the 8-point ordinal scale for clinical severity status.

16.2.1.3. Incidence of All-Cause Mortality through Day 29

The third key secondary efficacy endpoint is the incidence of all-cause mortality through Day 29, defined as the proportion of patients having died due to any cause before or on Day 29. Patients’ alive/death status by Day 29 will be determined based on data captured on the *Death Details* page of the eCRF. If a patient does not have any data captured on the *Death Details* page of the eCRF by Day 29 but his/her ‘subject status’ captured on the *Contact* page of the eCRF at Day 29 is alive or he/she had some data captured on any other page of the eCRF on or after Day 29, he/she will be considered alive on Day 29.

Refer to Section 16.2.2.1 for handling of missing alive/death through Day 29 status.

[figure not shown]
16.2.1.4. Distribution of Patients across the Categories of the 8-point Ordinal Scale for Clinical Severity at Days 8, 15, and 29

An ‘other secondary efficacy endpoint’ is the distribution of patients across the categories of the 8-point ordinal scale for clinical severity at Days 8, 15, and 29 i.e., the proportion of patients in each category of the 8-point ordinal scale for clinical severity at Days 8, 15, and 29. It is to be noted that patients with a score of 7 discharged to hospice care will be pooled with patients with a score of 1 (death) for this ‘other secondary efficacy endpoint’.

Refer to Section 16.1.1 for the description of the 8-point ordinal scale and to Section 16.2.2.1 for handling of missing ordinal scale scores.

16.2.1.5. Worst Post-Baseline Score on 8-point Ordinal Scale from Baseline to Day 29

An ‘other secondary efficacy endpoint’ is the worst post-baseline score (lower scores are worse) through Day 29 in the 8-point ordinal scale (refer to Section 16.1.1), derived from all scores recorded after baseline up to and including Day 29. It is to be noted that patients with a score of 7 discharged to hospice care will be considered as having a

score of 1 (death) instead of a score of 7 for this ‘other secondary efficacy endpoint.

Refer to Section 16.2.2.2 for handling of missing ordinal scale scores.

16.2.1.6. Number of ICU Days from Day 1 through Day 29

An ‘other secondary efficacy endpoint’ is the number of ICU days from Day 1 through Day 29. This endpoint will be considered as an ordinal endpoint.

For each patient, the number of ICU days from Day 1 through Day 29 will be derived based on the sum of the duration of any episodes of ICU admission between Day 1 and Day 29, inclusively, for patients who were alive on Day 29. Episodes of ICU admission will be identified based on data recorded on the *Hospitalization* page of the eCRF, where *Hospitalization Status* is recorded as *ICU/HDU*. For patients who were discharged to hospice care or died before or on Day 29, the number of ICU days from Day 1 through Day 29 will be set to 30 (worst possible scenario).

The duration, in days, of an episode of ICU admission will be derived as follows:

- Duration of an episode of ICU admission (days) = (Date of ICU discharge – Date of ICU admission) + 1

[figure not shown]
If the start date of an episode of ICU admission is prior to Day 1, it will be set to the date of Study Day 1 (refer to Section 6.1) when deriving ICU duration for that episode.

If an episode of ICU admission is ongoing at Day 29 or at the time of analysis, the stop date of the admission will be set to the minimum of:

- The start date of any subsequent ICU admission;
- Day 29;
- The data cut-off date for the analysis.

If there are any overlapping dates of ICU admission, a Day will only be counted once when deriving the overall number of ICU days for a patient. For example, if a patient has a record where the start and stop Study Days of the ICU/HDU admission are Day 3 and Day 10, respectively, and another record where the start and stop Study Days of ICU/HDU admission are Day 9 and Day 12, respectively, Days 9 and 10 will be counted only once in the overall number of ICU days for that patient.

Refer to Section 16.2.2.2 for handling of missing number of ICU days from Day 1 through Day 29.

16.2.1.7. Number of Invasive Mechanical Ventilator Days from Day 1 through Day 29

For each patient, the ‘other secondary efficacy endpoint’ of the number of invasive mechanical ventilator days from Day 1 through Day 29, inclusively, will be considered as an ordinal endpoint and derived similarly to the number of ICU days from Day 1 through Day 29 (refer to Section 16.2.1.6) but using the data collected on the *Supplemental Oxygen and Mechanical Ventilation* page of the eCRF where *Type of supplemental oxygen* is recorded as *Invasive Mechanical Ventilation*.

Refer to Section 16.2.2.2 for handling of missing number of invasive mechanical ventilation days from Day 1 through Day 29.

16.2.1.8. Incidence of Patients with Clinical Recovery by Days 8, 15, and 29

[figure not shown]
An ‘other secondary efficacy endpoint’ is the incidence of patients with clinical recovery at Days 8, 15, and 29, defined as the proportion of patients being fit for discharge (i.e., patients achieving a score of 6, 7, or 8 on the 8-point ordinal scale for clinical severity; refer to Section 16.1.1) at Days 8, 15, and 29, respectively, as per data recorded on the *Ordinal Scale for Clinical Severity* page of the eCRF. It is to be noted that patients with a score of 7 discharged to hospice care will not be considered as being fit for discharge for this ‘other secondary efficacy endpoint’.

Refer to Section 16.2.2.1 for handling of missing clinical recovery status by Days 8, 15, and 29.

16.2.1.9. Incidence of Patients with Sustained Clinical Recovery as Confirmed by Day 60 Follow-up

An ‘other secondary efficacy endpoint’ is the incidence of patients with sustained clinical recovery as confirmed by Day 60 follow-up, defined as the proportion of patients considered as being fit for discharge (i.e., achieving a score of 6, 7, or 8 on the 8-point ordinal scale for clinical severity) through Day 29, without re-hospitalization by Day 60 (refer to Section 16.1.1), as per the *Ordinal Scale for Clinical Severity* and *Hospitalization* pages of the eCRF. It is to be noted that patients with a score of 7 discharged to hospice care before or on Day 29 will not be considered as being fit for discharge for this ‘other secondary efficacy endpoint’.

Similarly to the primary efficacy endpoint, patients achieving a score of 6 on the ordinal scale for clinical severity before or on Day 29 will be considered as having sustained clinical recovery if they have no worsening of their ordinal scale score by Day 60 (i.e., a score < 6 on the ordinal scale for clinical severity) or were discharged from the hospital after Day 29 and were not re-hospitalized by Day 60.

Refer to Section 16.2.2.1 for handling of missing sustained clinical recovery as confirmed by Day 60 status.

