4.3. PRIMARY ANALYSIS

The primary analysis for a candidate agent will take place after:

- Approximately 350 patients have been randomized to the candidate agent plus SoC active arm of the sub-protocol of interest and approximately 350 patients have been randomized to the shared placebo plus SoC control arm of the sub-protocol of interest (refer to Section 4.5), and last patient randomized into one of these two arms is from the sub-protocol of interest, because if the last randomized patient is from a sub-protocol other than the one of interest, the patient’s treatment arm will automatically be unblinded since those patients can only be included in the shared placebo plus SoC control arm of the sub-protocol of interest;
- The last patient randomized to that candidate agent plus SoC treatment arm or its concurrent shared placebo plus SoC control arm have had the opportunity to complete the Day 29 study visit or discontinued from study before or on the Day 29 study visit;
- Sponsor authorization of this SAP;
- Sponsor authorization of the analysis sets (refer to Section 5.3);
- Interim or final database lock of each sub-protocol contributing to the shared control group of the candidate agent, as applicable;
- Interim database lock of the concerned candidate agent database (refer to DM Interim Database Lock Plan).

The data cut-off date will be the date the last patient completed the Day 29 study visit or discontinued from the study before or on the Day 29 study visit, whichever occurs first.

With the following exception, all planned analyses identified in this SAP will be performed by CCI Biostatistics at the time of the primary analysis of a sub-protocol. The exception is the summary and analysis of the secondary efficacy endpoint incidence of sustained clinical recovery as confirmed by Day 60 (refer to Section 16.2.1.9) which will be performed at the time of the final analysis of a sub-protocol (refer to Section 4.4).

For each sub-protocol, additional outputs to be produced at the time of the primary analysis may be specified in sub-protocol SAPs.

CCI [Redacted]

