6. GENERAL CONSIDERATIONS

6.1. STUDY DAY

Study day will be calculated from the day of the first dose of the study drug for patients who received at least one dose of study drug and from the day of randomization for randomized patients who were never dosed, and will be used to show start/stop day of assessments and events.

Study day will be computed as follows:

- Study Day = (Date of interest – Date of first dose of study drug/randomization, as appropriate) + 1 if the date of interest is on or after the date of first dose of study drug/randomization, as appropriate;
- Study Day = (Date of interest – Date of first dose of study drug/randomization, as appropriate) if the date of interest is prior to the date of first dose of study drug/randomization, as appropriate.

Based on these formula, Study Day 1 will be the day of the first dose of the study drug for patients who received at least one dose of study drug and the day of randomization for randomized patients who were never dosed.

In the situation where the date of interest is partial or missing, Study Day and any corresponding durations will be considered as missing in the analyses and the date of interest will be presented as partial or missing in the listings.

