6.3. UNSCHEDULED VISITS, RETESTS, DISCHARGE, AND EARLY TERMINATION DATA

For by-visit summaries, data recorded at the nominal visit will be presented. That is, unscheduled visits will not be included in by-visit summaries but might contribute to the baseline timepoint (refer to Section 6.2) and/or worst/maximum/minimum post-baseline value, where required (e.g., shift table).

In case of a retest when retest is defined as having a blood sample tested twice, the latest available measurement for that blood sample will be used for the by-visit summaries. In case of a retest when retest is defined as having two blood samples collected on the same day, results from the last blood sample will be used for the by-visit summaries.

Refer to Section 6.4 for the conventions to map discharge and early termination data to protocol-defined visit windows. Discharge and early termination data might also contribute to the worst/maximum/minimum post-baseline value, where required (e.g. shift table).

Listings will include all scheduled, unscheduled, retest, discharge, and early discontinuation data.

CCI

PPD

Version Number: Amendment 1, v1.0
Version Date: 23Apr2021

CCI

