16.2.2. MISSING DATA IMPUTATION METHOD FOR SECONDARY EFFICACY ENDPOINTS

16.2.2.1. Binary Endpoints

For the *incidence of oxygen-free recovery at Day 29* endpoint, the algorithm defined in Section 16.2.1.1 will first be applied. Then, patients with a missing oxygen-free recovery status at Day 29 will be considered as not having met the event for this key secondary efficacy endpoint.

For the *incidence of patients with ≥ 2-point improvement from baseline or fit for discharge on the ordinal scale at Day 29* endpoint (refer to Section 16.2.1.2), patients with a missing ordinal scale score at Day 29 due to patient’s death, discontinuation from study before or on Day 29 or for any other reason (with the following exception) will be considered as not having met the event at Day 29 for that key secondary endpoint. The only exception is for patients with a missing ordinal scale score at Day 29 for which the latest non-missing ordinal scale score before Day 29 was 7 (but not discharge to hospice care) or 8. These patients will be assumed to be fit for discharge at Day 29 and so, as having met the event.

For the *incidence of all-cause mortality through Day 29* endpoint (refer to Section 16.2.1.3), patients with an unknown alive/death status at Day 29 due to discontinuation from study for a reason other than death or missing data will be considered as alive in the analysis, exception of patients for who the last-missing ordinal scale score was 7 and that have been discharged to hospice care before discontinuing from study before Day 29. These patients will be considered as dead at Day 29 for the main analysis of this key secondary efficacy endpoint.

[figure not shown]
For the *clinical recovery by Day 8* endpoint (refer to Section 16.2.1.8), any patient who died before or on Day 8, discontinued from study before or on Day 8 or with missing clinical recovery status at Day 8 will be considered as not having clinical recovery by Day 8. Missing *clinical recovery by Days 15 and 29* will be handled similarly.

For the *sustained clinical recovery as confirmed by Day 60* follow-up endpoint (refer to Section 16.2.1.9), any patient who died before or on Day 60, discontinued study before Day 60 or with a missing 8-point ordinal scale score at Day 60 will be counted as not having sustained clinical recovery.

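### Oxygen-free recovery at Day 29 counts a recovered patient as a failure when the in-window Day 29 visit fell on Days 26-28 and no eCRF record is dated Day 29 or later at the primary-analysis cut-off

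*SAP*

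**What the plan says.** Master SAP 16.2.1.1 builds oxygen-free recovery from three components: alive, discharged and oxygen-free at Day 29. Under step 1, a patient with no Death Details entry by Day 29 but "with some data captured on any other page of the eCRF on or after Day 29 will be considered to be alive". No other route to alive status is given.

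The same section then says: "Should the status of one of the three criteria be missing while the two other criteria are fulfilled or missing", the endpoint is missing. Scenario 5 in its table is exactly this case: alive status missing, the other two criteria met. Section 16.2.2.1 closes the chain: "patients with a missing oxygen-free recovery status at Day 29 will be considered as not having met the event".

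For mortality, 16.2.1.3 has an additional route, through the Contact form. A patient without a death record is alive if the subject status on that form's "page of the eCRF at Day 29 is alive or he/she had some data captured on any other page of the eCRF", dated from Day 29 onward.

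The Day 29 visit has a window of ±3 days in the Master Protocol 1.3 example schedule and in the COV-01-004 schedule (section 1.2), so Days 26 to 32 comply. Master SAP 6.1 counts days by calendar date: "Study Day = (Date of interest – Date of first dose of study drug/randomization, as appropriate) + 1". For the primary analysis, Master SAP 4.3 says: "The data cut-off date will be the date the last patient completed the Day 29 study visit", or discontinued by then.

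**The concern.** Take a patient scored 8 and off oxygen at a compliant visit on Day 27, whose Day 60 contact has not yet happened at the cut-off. Recovery has been documented, yet step 1 finds no evidence of life and the patient becomes a failure. The other two key secondary endpoints do not penalise this patient. Mortality accepts the Contact page and, failing that, 16.2.2.1 counts unknown vital status as alive except after hospice discharge. The improvement or fit-for-discharge endpoint is met by the score of 8, and 16.2.2.1 would credit that score even if the Day 29 value were treated as missing.

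Oxygen-free recovery is the first test after the primary endpoint in the fixed sequence (Master SAP 7.4). If it misses significance, the other two key secondary endpoints, including mortality, get nominal p-values only.

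No planned analysis repairs the recoding. The multiple-imputation sensitivity analysis in 16.2.4 covers only patients who discontinued by Day 29, and these patients did not. The final-analysis outputs listed in Master SAP 4.4 do not include this endpoint, and the COV-01-004 SAP (section 4) adds only safety outputs, so Day 60 contacts that arrive later do not correct it.

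**Working it through.** **1. The plan's own figure.** Inputs from Master SAP 7.1 and 7.3: control rate 65%, increase 9.7 points (so 74.7%), n = 350 per arm, two-sided alpha 0.05.

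Power = Φ{[d − 1.96·√(2p̄(1−p̄)/n)] / √(p₀(1−p₀)/n + p₁(1−p₁)/n)}, with d = p₁ − p₀ and p̄ the mean of the two rates.

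Here p̄ = 0.6985, the first root is 0.03469 and the second is 0.03450. Then (0.097 − 1.96 × 0.03469)/0.03450 = 0.84 and Φ = 0.800. The stated 80% reproduces.

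**2. Who is affected.** A recovered patient is recoded only if both of these hold:
- the Day 29 visit fell on Days 26-28 (share e);
- no eCRF record is dated Day 29 or later at the cut-off (share L).

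The share of recovered patients recoded is q = e × L, taken as equal in both arms.

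**3. Inputs the documents do not give (assumptions).**
- e: 10% to 43%. The upper value is 3/7, visits spread evenly over the seven-day window.
- L: patients randomized in about the last 60 − 29 = 31 days before the cut-off have no Day 60 visit. With uniform accrual over 6 to 12 months, L = 31/(30.4 × 6) = 17.0% to 31/(30.4 × 12) = 8.5%. This also supposes that none of them has any other record dated Day 29 or later, such as an adverse event, medication or hospitalization entry.

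**4. Effect.** Each rate becomes p(1 − q), so the difference shrinks by the same factor.

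| Accrual | e | q | Rates | Difference | Power |
|---|---|---|---|---|---|
| 12 months | 10% | 0.85% | 64.4% vs 74.1% | 9.6 points | 78.9% |
| 12 months | 25% | 2.1% | 63.6% vs 73.1% | 9.5 points | 77.2% |
| 6 months | 25% | 4.25% | 62.2% vs 71.5% | 9.3 points | 74.3% |
| 6 months | 43% | 7.3% | 60.3% vs 69.3% | 9.0 points | 70.3% |

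At the 65% control rate, q of 0.85% to 7.3% means 0.65 × q = 0.6% to 4.7% of all control patients are wrongly failed.

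**The case against.** **Day 29 may mean the visit, not the date.** Master SAP 6.3 says: "For by-visit summaries, data recorded at the nominal visit will be presented", and Appendix 2 lists Day 29 among the nominal visits. If step 1 meant the nominal visit, a visit held on Day 27 would satisfy it and the problem would vanish. But 6.3 limits that convention to by-visit summaries, and step 1 does not adopt it. The wording of 16.2.1.3 points the other way: its Contact-page route adds something to the route through later data only if it can rest on a record dated before Day 29. Conversely, if Day 29 is a calendar date everywhere, a Day 27 score is not a Day 29 score in step 2, nor a Day 27 Contact entry a Day 29 status for mortality. Copying the mortality rule alone would then not cure the case. This part of the objection stands, and it is why the fix must also define the term.

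**Missing as failure is deliberate.** Protocol 9.3.4 fails patients whose missing data prevent their status from being defined. That is a legitimate choice, but a patient seen in window with every component recorded does not obviously fit it.

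**Reach.** COV-01-001 and COV-01-005 have no primary analysis and no efficacy inference, and are analysed after Day 60 or discontinuation. The testing consequence is confined to COV-01-004, whose SAP takes over the master efficacy analyses unchanged. This stands.

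**Stronger readings a reader might infer.** One is that every patient seen on Days 26-28 fails; with q = 3/7 the rates would be 37.1% vs 42.7% and power 32%. The text does not support this, since step 1 accepts any eCRF page at any date from Day 29 on. Another is that earlier patients who missed the Day 60 contact add to the count. The documents do not support this either: an unreachable patient is considered withdrawn (Protocol 7.3), the discontinuation date goes on the Disposition page (Master SAP 9.1.1), and a date after Day 29 is itself qualifying data.

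**Conclusion.** The gap is real but narrow. As worded, step 1 can turn a documented, in-window recovery into a failure when the visit fell on Days 26-28 and nothing is dated later at the cut-off. The cost is a modest loss of power on the first key secondary test, from 80% to about 79-70%, and understated recovery rates in both arms.

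The size rests on assumed accrual of 6-12 months and 10-43% early-window visits. The 70% figure needs six-month accrual, evenly spread visits and no other dated record for any affected patient, all together, so it should be read as the worst case. The finding also depends on reading Day 29 in step 1 as a calendar day, which the SAP neither states nor excludes. A reader might infer bias between arms; the documents give no reason why visit day would differ by arm, and no direction can be shown. The wording should still be corrected before the COV-01-004 primary analysis.

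**What to change.** In Master SAP 16.2.1.1 step 1, use the 16.2.1.3 rule: a patient is alive at Day 29 if there is no death record by Day 29 and either the Contact-page status at the Day 29 visit is alive or any eCRF data are dated on or after Day 29. In both sections, state that a status or score at Day 29 means the one from the nominal Day 29 visit within its ±3-day window.

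The cost is a short SAP edit and a line of code. The Contact page is already collected and already used for mortality. The downside is that an unreported death in the up to three days after an early-window visit would be missed, as it already is for mortality.
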